### **7.2 Statistical Methods**

A t-test will be used to compare the two arms of the study. We will apply other statistical methods as per Ochsner's statistics team & researchers.

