Study Regimen	Double-blind, randomized controlled clinical trial to test the efficacy of IPACK on postoperative opioid consumption, patient satisfaction, pain scores, mobility, and several other secondary outcomes in adults undergoing primary unilateral TKA. Enrolled patients will be randomized to either continuous ACB with IPACK or to continuous ACB with sham subcutaneous saline injection. Outcomes assessors and patients will be blinded to the intervention.
Duration of administration	Single preoperative IPACK block
Reference therapy	No IPACK block/sham subcutaneous saline injection
Statistical Methodology	Descriptive statistics per Ochsner statisticians

CONFIDENTIAL

This material is the property of Ochsner Clinic Foundation. Do not disclose or use except as authorized in writing by the study sponsor

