# **3 Study Design**

## **3.1 General Design**

Double blinded, randomized controlled trial. All patients who present for primary, unilateral tricompartment TKA will be screened for inclusion. Consecutive patients who meet preset inclusion and exclusion criteria will be recruited either on day of surgery or in the preoperative anesthesia clinic by one of the study investigators. Written consent will be obtained for study participation. Patients who participate will be randomized into one of two treatment arms: continuous ACB with IPACK block versus continuous ACB with sham subcutaneous saline injection. Randomization will be done using the website random.org's Coin Flipper, selecting the Susan B Anthony coin, and flipping 5 coins. Majority heads will be randomized to receive the IPACK block whereas majority tails will be randomized to receive the sham subcutaneous injection. See Attachment A for an example of this website.

CONFIDENTIAL

This material is the property of Ochsner Clinic Foundation. Do not disclose or use except as authorized in writing by the study sponsor

Only the regional anesthesiologist performing the block will know the randomization status. The study participants, outcome assessors/researchers, other anesthesia personnel, surgeons, physician assistants, and nurses will be blinded to the treatment arm. All patients will receive sedation with midazolam and/or fentanyl titrated to comfort during block procedures. Per our standard practice at Ochsner Medical Center, all patients will have either spinal or combined spinal-epidural anesthesia with mepivacaine 1.5% as the primary anesthetic during the surgery and sedation with propofol titrated to comfort. Also per our standard practice at Ochsner Medical Center, multimodal therapy will include ketamine 0.25mg/kg IV (up to 50mg) intraoperatively, dexamethasone 8mg IV intraoperatively, pregabalin 150mg PO preoperatively (adjusted to 75mg for age over 70) followed by 75mg nightly (or home gabapentin dose), acetaminophen 1000mg IV followed by 100mg PO every 6 hours postoperatively, and celecoxib 400mg PO on POD #0 followed by 200mg PO daily.

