### **3.2 Primary Study Endpoints**

- Cumulative opioid consumption (morphine equivalents) in the first 24 hours

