## **4.2 Exclusion Criteria**

- Contraindication to regional anesthesia or peripheral nerve blocks
- Allergy to local anesthetics
- Allergy to NSAIDs
- Chronic renal insufficiency with Cr > 1.4 or GFR < 60
- Have chronic pain that is not related to their knee joint
- Have been using opioids on a chronic basis (daily or almost daily opioid use for 3 months or longer)
- Have a pre-existing peripheral neuropathy involving the operative site
- Body mass index greater than or equal to 40

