### **5.3 Method for Assigning Subjects to Treatment Groups**

Subjects will be randomized to one treatment arm at time of trial enrollment. Randomization will be done using the website random.org's Coin Flipper, selecting the Susan B Anthony coin, and flipping 5 coins. Majority heads will be randomized to receive the IPACK block whereas majority tails will be randomized to receive the sham subcutaneous injection.

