## **7 Statistical Plan**

### **7.1 Sample Size Determination**

Prior published literature demonstrates analgesic equivalence between adductor canal block and femoral nerve block. An institutional retrospective study here showed a 38.8% effect difference between femoral nerve block with and without IPACK. Using this information, for an effect size of 0.4, power of 0.8, and significance level of 0.05 we determined a sample size of 64 patients. Assuming a dropout rate of 10%, we will include 72 patients in this study with approximately 36 patients per study arm.

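### Section 7.2 compares the arms with a valid but unadjusted t-test; pre-specifying adjustment for age, known for every patient, would be a small, low-cost efficiency gain

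*Combined protocol and SAP*

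**What the plan says.** The primary endpoint in section 3.2 is "Cumulative opioid consumption (morphine equivalents) in the first 24 hours", a continuous quantity. For its analysis, section 7.2 says "A t-test will be used to compare the two arms of the study". It then adds "We will apply other statistical methods as per" the institution's statistics team and researchers, without naming a model or covariate. The Study Summary gives the methodology only as "Descriptive statistics per Ochsner statisticians".

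Allocation is decided patient by patient with five virtual coins: "Majority heads will be randomized to receive the IPACK block" (section 5.3, repeated in 3.1). No blocking or stratification is described.

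Age enters the protocol twice. It is an inclusion criterion (section 4.1), and it determines a background analgesic dose in both arms: "pregabalin 150mg PO preoperatively (adjusted to 75mg for age over 70" (section 3.1). Opioid history enters through the exclusion "Have been using opioids on a chronic basis (daily or almost daily opioid use for 3 months or longer" (section 4.2). No section lists baseline variables to be recorded for analysis.

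**The concern.** For a continuous outcome, a linear model that includes a prognostic baseline variable usually estimates the treatment difference more precisely than a two-sample t-test. Nothing in the allocation scheme balances the arms on age. The plan gives age a plausible link to the outcome, because background analgesia changes at age 70. Age is in hand for every patient before randomization, so leaving it out may give up some precision in a trial of about 72 patients.

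The open-ended second sentence of 7.2 adds a smaller issue. Section 8.4 places unblinding at the end of the study, to allow the group analysis. If covariates are not named before then, an adjusted analysis could be chosen with the results in view.

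**Working it through.** **Inputs.** From 7.1: effect size 0.4, power 0.8, significance level 0.05, 64 patients before dropout, 10% dropout, 72 enrolled. Assumed: the effect size is a standardized mean difference d, the test is two-sided, and the 64 evaluable patients are split 32 and 32. The documents give neither an R-squared between age and 24-hour opioid use nor the share of patients over 70; both are varied below.

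**The plan's own figure.** Normal formula per arm: 2 × (1.960 + 0.842)² / 0.4² = 98.1, so 99 per arm and 198 in total. The stated 64 does not reproduce for a two-arm t-test at d=0.4. The dropout step does: 64 / 0.9 = 71.1, so 72. With 32 per arm, 80% power is reached at d of about 0.71. Both d=0.4 (as stated) and d=0.71 (what 64 patients can detect) are therefore carried forward.

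**Power with one covariate.** Outcome SD is set to 1 and N = 64.

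- t-test: SE = √(4/64) = 0.2500, with 62 degrees of freedom.
- Linear model with k = 1 covariate: SE = √[(1 − R²) × (4/64) × (1 + k/(N − k − 3))] = √[(1 − R²) × 0.0625 × 61/60], with 61 degrees of freedom. The factor 61/60 is the average cost of chance imbalance in the covariate.
- Power comes from the noncentral t distribution with noncentrality d/SE.

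| Analysis | SE | Power, d=0.4 | Power, d=0.71 |
|---|---|---|---|
| t-test | 0.2500 | 35.0% | 79.8% |
| Model, R²=0 | 0.2521 | 34.5% | 79.2% |
| Model, R²=0.02 | 0.2495 | 35.1% | 80.0% |
| Model, R²=0.05 | 0.2457 | 36.1% | 81.2% |
| Model, R²=0.10 | 0.2391 | 37.7% | 83.2% |
| Model, R²=0.20 | 0.2255 | 41.5% | 87.3% |

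**Break-even.** On the standard error alone, the model gains once 1 − R² falls below 60/61, that is R² above 0.016. Counting the lost degree of freedom as well, the two power curves cross at about 0.017. With two covariates the crossing is at about 0.034.

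**Equivalent sample size.** 64 × (60/61) / (1 − R²) gives about 64, 66, 70 and 79 patients for R² of 0.02, 0.05, 0.10 and 0.20.

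**Chance imbalance on age.** With 36 per arm and a share p over 70, the SD of the difference in shares is √[2p(1 − p)/36]. For assumed p of 0.25, 0.35 and 0.45 this is 0.102, 0.112 and 0.117. The probability that the arms differ by 15 points or more is then 14%, 18% and 20%.

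**Could adjustment rescue the sample size?** Reaching 80% power at d=0.4 with 32 per arm needs R² = 1 − (32 × 0.16) / [2 × (1.960 + 0.842)²] = 1 − 5.12/15.70 = 0.67, far outside the range considered here.

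**The case against.** The strongest reply is that nothing here is an error. Under simple randomization the t-test is unbiased, and its standard error already allows for chance imbalance. That stands in full. A reader might infer from the unstratified allocation that the t-test result will be biased by an age imbalance. The documents do not support this. An imbalance in a given trial shifts the estimate only if age is prognostic, and over repeated allocations the shift averages to zero. Nor is a large imbalance likely: 14% to 20% for a 15-point difference, at an assumed share over 70.

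A second reply is that the benefit rests on an R-squared that nobody has stated. That also stands. The pregabalin rule does not show that age predicts opioid use. It applies equally in both arms, and its effect could add to or offset any direct effect of age. Excluding chronic opioid users also removes one likely strong predictor. The gain may be close to nil, and below the break-even point it is a slight loss, so the precision is not strictly free.

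Third, it is tempting to say that preoperative opioid use is also available as a covariate. Sections 4.2 and 5.6 require only that daily or almost daily use for 3 months or longer be ruled out. Screening can do that without recording occasional use in those enrolled. Age is different: eligibility and the pregabalin dose both require it, although its listing as an analysis variable is inferred.

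Finally, 7.2 leaves other methods open, so adjustment is unspecified rather than excluded. That is correct, but it is a reason to name the covariate now.

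**Conclusion.** The point holds as a modest efficiency improvement. For R-squared between 0.02 and 0.20, adjusting for age adds from about 0 to 6.5 power points at d=0.4 and from about 0 to 7.5 at d=0.71. If age carries no information, the cost is about 0.5 and 0.7 points respectively. These figures assume 64 evaluable patients in equal arms, a two-sided test, a standardized effect size and a linear age effect; the R-squared range is an assumption throughout.

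The change corrects no bias and leaves type I error where it was. A reader might also infer that adjustment would make up for the low power at the stated effect size. It would not: that would take an R-squared of about 0.67. The mismatch between 64 patients and an effect size of 0.4 is a separate and larger problem in 7.1.

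**What to change.** In 7.2, before unblinding, name as the primary analysis a linear model of 24-hour morphine equivalents on treatment arm and age as a continuous variable. Report the treatment coefficient with its confidence interval, and keep the unadjusted t-test as a supportive analysis. State that age at enrolment is recorded for every randomized patient.

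Add preoperative opioid use as a second covariate only if it is recorded in a defined way for every patient before randomization. That would need a case report form item that the protocol does not now describe, and it would raise the break-even R-squared to about 0.034.

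The cost for age alone is a few sentences of SAP text, one degree of freedom and a second reported estimate.

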### **7.3 Subject Population(s) for Analysis**

- Unilateral, primary tricompartment total knee arthroplasty
- Age 18 years or older
- ASA I-III
- Eligible for spinal or combined spinal epidural anesthetic
- Able to speak, read, and understand English
- Willing to participate in the trial
- Do not meet any exclusion criteria previously defined in this protocol

## **8 Safety and Adverse Events**

### **8.1 Definitions**

#### ***Adverse Event***

CONFIDENTIAL

This material is the property of Ochsner Clinic Foundation. Do not disclose or use except as authorized in writing by the study sponsor

An **adverse event** (AE) is any symptom, sign, illness or experience that develops or worsens in severity during the course of the study. Intercurrent illnesses or injuries should be regarded as adverse events. Abnormal results of diagnostic procedures are considered to be adverse events if the abnormality:

- results in study withdrawal
- is associated with a serious adverse event
- is associated with clinical signs or symptoms
- leads to additional treatment or to further diagnostic tests
- is considered by the investigator to be of clinical significance

### ***Serious Adverse Event***

Adverse events are classified as serious or non-serious. A **serious adverse event** is any AE that is:

- fatal
- life-threatening
- requires or prolongs hospital stay
- results in persistent or significant disability or incapacity
- a congenital anomaly or birth defect
- an important medical event

Important medical events are those that may not be immediately life threatening, but are clearly of major clinical significance. They may jeopardize the subject, and may require intervention to prevent one of the other serious outcomes noted above. For example, drug overdose or abuse, a seizure that did not result in in-patient hospitalization, or intensive treatment of bronchospasm in an emergency department would typically be considered serious.

All adverse events that do not meet any of the criteria for serious should be regarded as **non-serious adverse events**.

### ***Adverse Event Reporting Period***

The study period during which adverse events must be reported is normally defined as the period from the initiation of any study procedures to the end of the study treatment follow-up. For this study, the study treatment follow-up is defined as 30 days following the last administration of study treatment.

### ***Preexisting Condition***

A preexisting condition is one that is present at the start of the study. A preexisting condition should be recorded as an adverse event if the frequency, intensity, or the character of the condition worsens during the study period.

### ***General Physical Examination Findings***

At screening, any clinically significant abnormality should be recorded as a preexisting condition. At the end of the study, any new clinically significant findings/abnormalities that meet the definition of an adverse event must also be recorded and documented as an adverse event.

### ***Post-study Adverse Event***

CONFIDENTIAL

All unresolved adverse events should be followed by the investigator until the events are resolved, the subject is lost to follow-up, or the adverse event is otherwise explained. At the last scheduled visit, the investigator should instruct each subject to report any subsequent event(s) that the subject, or the subject's personal physician, believes might reasonably be related to participation in this study. The investigator should notify the study sponsor of any death or adverse event occurring at any time after a subject has discontinued or terminated study participation that may reasonably be related to this study. The sponsor should also be notified if the investigator should become aware of the development of cancer or of a congenital anomaly in a subsequently conceived offspring of a subject that has participated in this study.

### ***Abnormal Laboratory Values***

A clinical laboratory abnormality should be documented as an adverse event if any one of the following conditions is met:

- The laboratory abnormality is not otherwise refuted by a repeat test to confirm the abnormality
- The abnormality suggests a disease and/or organ toxicity
- The abnormality is of a degree that requires active management; e.g. change of dose, discontinuation of the drug, more frequent follow-up assessments, further diagnostic investigation, etc.

### ***Hospitalization, Prolonged Hospitalization or Surgery***

Any adverse event that results in hospitalization or prolonged hospitalization should be documented and reported as a serious adverse event unless specifically instructed otherwise in this protocol. Any condition responsible for surgery should be documented as an adverse event if the condition meets the criteria for and adverse event.

Neither the condition, hospitalization, prolonged hospitalization, nor surgery are reported as an adverse event in the following circumstances:

- Hospitalization or prolonged hospitalization for diagnostic or elective surgical procedures for a preexisting condition. Surgery should **not** be reported as an outcome of an adverse event if the purpose of the surgery was elective or diagnostic and the outcome was uneventful.
- Hospitalization or prolonged hospitalization required to allow efficacy measurement for the study.
- Hospitalization or prolonged hospitalization for therapy of the target disease of the study, unless it is a worsening or increase in frequency of hospital admissions as judged by the clinical investigator.

## ***8.2 Recording of Adverse Events***

At each contact with the subject, the investigator must seek information on adverse events by specific questioning and, as appropriate, by examination. Information on all adverse events should be recorded immediately in the source document, and also in the appropriate adverse event module of the case report form (CRF). All clearly related signs, symptoms, and abnormal diagnostic procedures results should recorded in the source document, though should be grouped under one diagnosis.

CONFIDENTIAL

All adverse events occurring during the study period must be recorded. The clinical course of each event should be followed until resolution, stabilization, or until it has been determined that the study treatment or participation is not the cause. Serious adverse events that are still ongoing at the end of the study period must be followed up to determine the final outcome. Any serious adverse event that occurs after the study period and is considered to be possibly related to the study treatment or study participation should be recorded and reported immediately.

### **8.3 Reporting of Serious Adverse Events**

#### **8.3.1 Study Sponsor Notification by Investigator**

A serious adverse event must be reported to the study sponsor by telephone within 24 hours of the event. A Serious Adverse Event (SAE) form must be completed by the investigator and faxed to the study sponsor within 24 hours. The investigator will keep a copy of this SAE form on file at the study site. Report serious adverse events by phone and facsimile to:

[name], [contact], [contact]

At the time of the initial report, the following information should be provided:

- Study identifier
- Study Center
- Subject number
- A description of the event
- Date of onset
- Current status
- Whether study treatment was discontinued
- The reason why the event is classified as serious
- Investigator assessment of the association between the event and study treatment

Within the following 48 hours, the investigator must provide further information on the serious adverse event in the form of a written narrative. This should include a copy of the completed Serious Adverse Event form, and any other diagnostic information that will assist the understanding of the event. Significant new information on ongoing serious adverse events should be provided promptly to the study sponsor

#### **8.3.2 EC/IRB Notification by Investigator**

Reports of all serious adverse events (including follow-up information) must be submitted to the EC/IRB within 10 working days. Copies of each report and documentation of EC/IRB notification and receipt will be kept in the Clinical Investigator's binder.

#### **8.3.3 FDA Notification by Sponsor**

The study sponsor shall notify the FDA by telephone or by facsimile transmission of any unexpected fatal or life-threatening experience associated with the use of the drug as soon as possible but no later than 7 calendar days from the sponsor's original receipt of the information.

CONFIDENTIAL

If a previous adverse event that was not initially deemed reportable is later found to fit the criteria for reporting, the study sponsor will submit the adverse event in a written report to the FDA as soon as possible, but no later than 15 calendar days from the time the determination is made.

#### **8.4 Unblinding Procedures**

Physicians performing the study intervention will not be blinded to the drug or technique. The study participants, outcome assessors/researchers, other anesthesia personnel, surgeons, physician assistants, and nurses will be blinded to the treatment arm. Unblinding will occur at the conclusion of the study in order to facilitate group analysis.

#### **8.5 Stopping Rules**

Not applicable.

#### **8.6 Medical Monitoring**

It is the responsibility of the Principal Investigator to oversee the safety of the study at his/her site. This safety monitoring will include careful assessment and appropriate reporting of adverse events as noted above, as well as the construction and implementation of a site data and safety-monitoring plan (see section 9 Auditing, Monitoring and Inspecting). Medical monitoring will include a regular assessment of the number and type of serious adverse events.

##### **8.6.1 Internal Data and Safety Monitoring Board**

##### **8.6.2 Independent Data and Safety Monitoring Board**

### **9 Data Handling and Record Keeping**

#### **9.1 Confidentiality**

Information about study subjects will be kept confidential and managed according to the requirements of the Health Insurance Portability and Accountability Act (HIPAA). Those regulations require a signed subject authorization informing the subject of the following:

- What protected health information (PHI) will be collected from subjects in this study
- Who will have access to that information and why
- Who will use or disclose that information
- The rights of a research subject to revoke their authorization for use of their PHI.

In the event that a subject revokes authorization to collect or use PHI, the investigator, by regulation, retains the ability to use all information collected prior to the revocation of subject authorization. For subjects that have revoked authorization to collect or use PHI, attempts should be made to obtain permission to collect at least vital status (i.e. that the subject is alive) at the end of their scheduled study period.

CONFIDENTIAL

This material is the property of Ochsner Clinic Foundation. Do not disclose or use except as authorized in writing by the study sponsor

## **9.2 Source Documents**

Source data is all information, original records of clinical findings, observations, or other activities in a clinical trial necessary for the reconstruction and evaluation of the trial. Source data are contained in source documents. Examples of these original documents, and data records include: hospital records, clinical and office charts, laboratory notes, memoranda, subjects' diaries or evaluation checklists, pharmacy dispensing records, recorded data from automated instruments, copies or transcriptions certified after verification as being accurate and complete, microfiches, photographic negatives, microfilm or magnetic media, x-rays, subject files, and records kept at the pharmacy, at the laboratories, and at medico-technical departments involved in the clinical trial.

